5.2 Exclusion criteria

Participants meeting **any** of the following criteria are not eligible for inclusion in this protocol:

- Onset of COVID-19 pneumonia symptoms (i.e. dyspnea/respiratory insufficiency) >14 days
- 2. On mechanical ventilation at the time of randomization
- 3. A $PaO_2/FiO_2 < 100 \text{ mmHg}$

- 4. Uncontrolled systemic infection (other than COVID-19)
- 5. Hypersensitivity to the active substance or to any of the excipients of the experimental drug
- 6. Total neutrophil count < 1500/mm³
- 7. Severe hepatic cirrhosis
- 8. History of chronic HBV or HCV infection
- 9. Known or active tuberculosis (TB) or a history of incompletely treated TB; suspected or know extrapulmonary tuberculosis
- 10. Moderate/severe heart failure (NYHA Class 3 or 4)
- 11. Any prior (within the defined periods below) or concurrent use of immunosuppressive therapies including but not limited to the following:
 - a. Anti-IL-6, anti-IL-6R antagonists or Janus kinase inhibitors (JAKi) in the past 30 days or plans to receive during the study period;
 - b. Cell-depleting agents (e.g., anti CD20) without evidence of recovery of B cells to baseline level;
 - c. Anakinra within 1 week of baseline; canakinumab within 8 weeks of baseline; abatacept within 8 weeks of baseline.
 - d. Tumor necrosis factor (TNF) inhibitors within 2-8 weeks (etanercept within 2 weeks, infliximab, certolizumab, golimumab, or adalimumab within 8 weeks), or after at least 5 half-lives have elapsed, whichever is longer;
 - e. Alkylating agents including cyclophosphamide (CYC) within 6 months of baseline;
 - f. Cyclosporine (CsA), azathioprine (AZA) or mycophenolate mofetil (MMF) or leflunomide or methotrexate within 4 weeks of baseline.
- 12. Pregnancy or lactation (Note: Women of childbearing age should use effective contraception/abstinence after treatment with mavrilimumab and for 3 months after the dosing)
- 13. Any serious medical condition or abnormality of clinical laboratory tests that, in the investigator's judgment, precludes the patient's safe participation in and completion of the study
- 14. In the opinion of the investigator, progression to death is imminent and highly likely within the next 24 hours, irrespective of the provision of treatments
- 15. Current participation in any other interventional investigational trials

6. Treatment plan

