The study will enroll patients who require hospitalization with supportive care for COVID-19 pneumonia, including supplemental oxygen. All patients will receive, in addition to the best available standard of care, mavrilimumab or placebo. One single dose of mavrilimumab or placebo will be given.

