6.6 Treatment assignment, randomization

At Randomization visit, all eligible subjects will be randomized via Interactive Response Technology (IRT) to one of the treatment arms. A designated site staff member other than the investigator or study staff involved in safety and efficacy assessments or eCRF completion will contact the IRT after confirming that the subject fulfills all the inclusion/exclusion criteria. The IRT will assign a randomization number to the participant, which will be used to link the participant to a treatment arm.

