and Regulation (EU) 2016/679 of the European Parliament and of the Council of 27 April 2016 on the protection of natural persons with regard to the processing of personal data and on the free movement of such data, and repealing Directive 95/46/EC (General Data Protection Regulation).

The name of the patient will not be asked by the promoter. A identification number will be automatically attributed to each patient enrolled in the trial. This number will identify the patient and must be included on all case report forms. In order to avoid identification errors, date of birth will also be reported on forms.

Information about common side effects already known about the investigational drug can be found in the Investigator's Brochure (IB). This information is included in the participant informed consent and should be discussed with the participant during the study as needed. Any new information regarding the safety profile of the investigational drug that is identified between IB updates will be communicated. New information might require an update to the informed consent and then must be discussed with the participant.

Women of childbearing potential must be informed that taking the study treatment may involve unknown risks to the fetus if pregnancy were to occur during the study and agree that in order to participate in the study they must adhere to the contraception requirements.

8. Visit schedule and assessments

The Assessment & Procedures Schedule (Table 1) lists all of the assessments when they are performed. All data obtained from these assessments must be supported in the participant's source documentation.

Participants should be seen or phoned for all visits/assessments as outlined in the assessment schedule (Table 1) or as close to the designated day/time as possible. Missed or rescheduled visits should not lead to automatic discontinuation. At the day of discharge from the hospital, all assessments in Table 1 should be conducted. In addition, contact information for the patient and/or legal representatives should be obtained for the follow-up visits.

Screening assessments are to be taken as indicated in Table 1 prior to dosing and are considered baseline measurements. Patients who meet the inclusion/exclusion criteria may be dosed immediately after obtaining the baseline measurements.

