8.2 Screening / screening failures

No rescreening will be permitted. Participants who sign an informed consent form and subsequently found to be ineligible prior to randomization will be considered a screen failure. The reason for screen failure should be recorded on the appropriate CRF. The demographic information, informed consent, and Inclusion/Exclusion pages must also be completed for screen failure participants. No other data will be entered into the clinical database for participants who are screen failures, unless the participant experienced a serious adverse event during the screening phase.

If the participant fails to be randomized, the IRT must be notified within 2 days of the screen fail that the participant was not randomized.

Participants who are randomized and fail to start treatment, e.g. participants randomized in error, will be considered an early terminator. The reason for early termination should be recorded on the appropriate CRF.

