8.5 Safety

Safety assessments are specified below with the assessment schedule detailing when each assessment is to be performed.

Laboratory evaluations

Clinically significant abnormalities must be recorded as either medical history/current medical conditions or adverse events as appropriate.

Presence SARS-CoV-2 virus

For the Screening inclusion criterion, SARS-CoV-2 virus should be measured by PCR or by other approved diagnostic methodology \leq 7days of Screening by local lab. Documentation of the method used should be available in the source notes.

Laboratory evaluations for Safety

Laboratory evaluations will be performed by the local lab.

Hematology

Hemoglobin, mean corpuscular volume (MCV), white blood cell count with differential, and platelet count will be measured according to the assessment schedule in Table 1.

Chemistry

Creatinine, total bilirubin, direct bilirubin, AST, ALT, alkaline phosphatase, lactate dehydrogenase, creatine kinase, troponin, total protein, glucose will be measured according to the assessment schedule in Table 1. If a given test is not available locally, this should be documented on the eCRF.

Additional markers of inflammation: high-sensitivity C-reactive protein (hsCRP), ferritin, D-dimer, and IL-6 (if locally available) should be collected in accordance with Table 1.

In the case where a laboratory range is not specified by the protocol, but a value is outside the reference range for the laboratory at screening and/or initial baseline, a decision regarding whether the result is of clinical significance or not shall be made by the Investigator (in consultation with the Promoter) and shall be based, in part, upon the nature and degree of the observed abnormality. In all cases, the Investigator must document in the source documents, the clinical considerations (i.e., result was/was not clinically significant and/or medically relevant) in allowing or disallowing the participant to continue in the study.

All patients with laboratory tests containing clinically significant abnormalities should be followed until the values return to within the normal ranges or until a clinical explanation is identified, even after study medication has discontinued.

Physical exam

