Adverse events of hepatic function abnormality of special interest are defined as any increase in ALT or AST to greater than $3 \times ULN$ and concurrent increase in bilirubin to greater than $2 \times ULN$. Concurrent findings are those that derive from a single blood draw or from separate blood draws taken within 8 days of each other. In the event of hepatic function abnormality where the etiology is unknown, timely follow-up investigations and inquiries should be initiated by the investigational site, based on medical judgment, to make an informed decision regarding the etiology of the event. Investigational product will not be administered to any subject reporting ALT or AST to greater than $3 \times ULN$ and concurrent increase in bilirubin to greater than $2 \times ULN$

Acute and Delayed Hypersensitivity Reactions

Biologic therapies are known to be associated with an increased risk of immediate and delayed hypersensitivity reactions as well as anaphylaxis. Anaphylaxis and severe hypersensitivity reactions are required to be reported within 24 hours of knowledge of the event, and ADA samples should be collected as possible.

Clinically Significant Pulmonary Abnormality

Any subject who develops new clinically significant pulmonary symptoms or signs should be referred to a qualified specialist for further specific assessment. Symptoms and signs triggering such referral include but are not limited to an increase in shortness of breath or difficulty breathing, exacerbation of current respiratory symptoms, or a significant

deterioration in dyspnea score. Subjects who are referred for evaluation by a specialist will undergo a diagnostic evaluation to determine the nature and origin of the pulmonary symptom(s)/sign(s) and to determine if PAP may be present. At the discretion of the investigator or specialist additional tests may be required such as a repeat chest x-ray, and/or a chest high resolution computed tomography scan, full PFTs including DLCO measurement, bronchoscopy with bronchoalveolar lavage, and cytological and/or ultrastructural evaluation of the cells recovered by lavage to identify findings consistent with a diagnosis of PAP. Any subject who has been referred for a specialist pulmonary evaluation may be instructed to stop the investigational product until the symptom(s) or sign(s) causing the referral have resolved.

Neutropenia

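### Section 10.1 forbids the only infusion above a set ALT/AST and bilirubin limit, but eligibility has no such limit, so a patient can be randomised and then barred from dosing

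*Protocol*

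**What the plan says.** Protocol section 6 (Treatment plan) fixes the regimen: "One single dose of mavrilimumab or placebo will be given".

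Section 10.1, Hepatic Function Abnormality, sets an absolute rule: "Investigational product will not be administered to any subject reporting ALT or AST to greater than" 3 × ULN together with bilirubin above 2 × ULN. It defines concurrence broadly: "Concurrent findings are those that derive from a single blood draw or from separate blood draws taken within 8 days of each other".

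Sections 5.1 and 5.2 contain no limit for ALT, AST or bilirubin. The liver-specific exclusions are severe cirrhosis and past chronic hepatitis B or C, which are diagnoses and not laboratory values. Exclusion 13 is a general clause: "Any serious medical condition or abnormality of clinical laboratory tests that" the investigator judges to rule out safe participation and completion. It names no test and no threshold.

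The path to treatment refers only to eligibility. Under section 6.6, designated site staff "contact the IRT after confirming that the subject fulfills all the inclusion/exclusion criteria". Section 8 adds: "Patients who meet the inclusion/exclusion criteria may be dosed immediately after obtaining the baseline measurements". Section 4 says the same in similar terms. None of the three mentions the limit in 10.1.

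**The concern.** A rule that withholds product has two possible uses: to stop a first dose or to stop later ones. Here there are no later ones, so the hepatic rule in 10.1 can only decide whether the patient receives the day 1 infusion. That makes it an entry criterion, but it is placed in the adverse-event section, where staff confirming eligibility before randomisation have no instruction to look.

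A patient with these liver values who meets 5.1 and 5.2 leaves the site two options:

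- **Dose the patient.** This breaches a mandatory safety rule of the protocol.
- **Withhold the dose after randomisation.** Section 8.2 then applies: "Participants who are randomized and fail to start treatment, e.g. participants randomized in error, will be considered an early terminator". Sections 11.1 and 11.2 base every efficacy analysis on patients who were randomised and dosed, so this patient drops out. Section 4 stops enrolment at the target number of randomised patients and makes no provision for a replacement.

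**Working it through.** **1. The texts side by side**

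| Question | Hepatic rule | Neutrophil rule |
|---|---|---|
| No-dosing limit in 10.1 | ALT or AST > 3 × ULN with bilirubin > 2 × ULN | ANC < 1.0 × 10⁹/L, which is 1000/mm³ |
| Laboratory exclusion in 5.2 | none | < 1500/mm³ |
| Can an eligible patient breach the 10.1 limit at screening? | yes | no, since 1000 < 1500 |

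The neutrophil rule has the same form and is fully covered by a stricter exclusion. The hepatic rule has no counterpart. That points to an omission and not to a decision to keep dosing rules separate from eligibility.

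**2. Do other provisions close the gap?**

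- Exclusion 13 rests on the investigator's judgement and has no link to the threshold in 10.1.
- The laboratory review in section 8.5 is also a judgement. It opens with "In the case where a laboratory range is not specified by the protocol", whereas for these tests 10.1 does specify a limit.

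Both may catch the patient. Neither has to.

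**3. Scale of the effect on the analysis**

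Inputs from section 11.1: 83% and 40% off oxygen by day 14, two-sided alpha 0.05, 90% power, 28 events, about 50 patients randomised 1:1.

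The plan's own figure first:

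- Hazard ratio = ln(1 − 0.83) / ln(1 − 0.40) = (−1.772) / (−0.511) = 3.469, so ln HR = 1.244.
- Schoenfeld events = 4 × (1.960 + 1.282)² / 1.244² ≈ 27.2, rounded up to 28. This reproduces the protocol.
- Power at d events = Φ(√d × 1.244 / 2 − 1.960). At d = 28 this is 90.8%.

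Now let k randomised patients go undosed. Expected events are (50 − k) × (0.83 + 0.40) / 2, with losses taken as equal across arms on average.

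| k undosed | Share of 50 | Expected events | Power |
|---|---|---|---|
| 0 | 0% | 30.75 | 93.2% |
| 1 | 2% | 30.1 | 92.7% |
| 2 | 4% | 29.5 | 92.2% |
| 4 | 8% | 28.3 | 91.1% |
| 5 | 10% | 27.7 | 90.5% |
| 6 | 12% | 27.1 | 89.9% |

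The protocol gives no baseline rate for this liver pattern, so k is an assumption. A range of 0 to 2 is used for the conclusion, and the further rows show where the margin ends. Expected events fall below 28 at k = 5, and power falls below 90% at k = 6.

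**The case against.** The strongest reply is that exclusion 13 already does the work. Taking part in this trial means receiving one infusion, so an investigator who knows that 10.1 forbids it could hardly also judge that the patient can safely take part and complete. The liver tests are in the screening sample, and section 8.5 asks the investigator to document the reasoning on abnormal values. On this view the conflict arises only if the site overlooks 10.1. That is true, but it is also the problem: nothing in the eligibility path sends the site to 10.1, and a mandatory limit should not depend on a discretionary clause that does not mention it.

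A second reply is that the sentence is left over from a repeat-dose protocol. The neighbouring neutropenia and pulmonary paragraphs also speak of continuing or pausing product. This may well be so. The sentence is nevertheless in force, applies to any subject, and under a single-dose design can affect only the day 1 infusion. If it was not intended, it needs deleting, so the text needs correcting either way.

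Some of the objection stands. The liver pattern may be rare. The target of 50 is approximate and section 10.3 ties the end of enrolment to interim results, so an undosed patient might in practice be made up. It is also unclear whether the 8-day concurrence window reaches back to ward results before consent, and the conclusion does not rely on that.

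**Conclusion.** The concern holds. Sections 10.1 and 5.1/5.2 are inconsistent: the only dose is forbidden at liver values that eligibility does not exclude. A patient can meet every entry criterion, be randomised, and then be either dosed in breach of the protocol or lost from the evaluable population.

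The statistical effect is small. Under the assumed 0 to 2 such patients, power goes from 93.2% to no lower than 92.2%, and the planned 90% is kept. The rule depends on values before dosing, so it is unrelated to arm and introduces no bias. The reasons to correct it are patient safety and the avoidance of randomised but untreated patients. The amendment should be made, though the trial's main conclusion does not depend on it.

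**What to change.** Add an exclusion to section 5.2, and to the synopsis list: ALT or AST above 3 × ULN with bilirubin above 2 × ULN, checked on the sample taken 0–24 hours before dosing and before the randomisation system is contacted. Keep exclusion 13 alongside it for other abnormalities. When wording the exclusion, state whether earlier results within the 8-day window count.

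If the sponsor does not intend these values to prevent dosing, the alternative is to delete the dosing sentence from 10.1. The exclusion is preferable because it keeps the safety rule and places it where it can act.

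The cost is wording only. Section 8.5 already lists ALT, AST and bilirubin for measurement on the Table 1 schedule, which has a screening sample before dosing. At most there is a rare extra screen failure, of a patient whom 10.1 would not allow to be treated anyway. No sample-size figure changes.

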10.2 Data Safety Monitoring Board

This study will include an external data safety monitoring board (DSMB) which in collaboration with the Writing Committee will perform safety data reviews after each increment of 10 evaluable patients has reached day 14 in order to provide a high level of safety surveillance for patients enrolled in the study. The DSMB will assess at defined intervals the progress of a clinical trial, safety data, and critical efficacy variables and recommend whether to continue, modify, or terminate a trial.

10.3 Safety Evaluation

The end of enrollment will be based on interim results, with continuation of enrollment or discontinuation of the study according to the response of patients to treatment. The follow-up according to the protocol is 3 months for each patient enrolled. The end of the study, including statistical analysis and drafting of the final report, is expected at 1 month from the last follow-up of the last patient enrolled. The study will be performed in approximately 3 months starting from the first patient enrolled (depending on the speed of enrollment).

11. Statistical considerations and data analysis

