3.3 Exploratory objectives and endpoints

Exploratory objectives	Exploratory endpoints
To evaluate the clinical efficacy of mavrilimumab compared to the control arm by clinical severity (i.e. mild vs	To evaluate the primary and secondary endpoints in different subgroups of patients:
moderate subgroup)	- mild respiratory failure: $PaO_2/FiO_2 \le 300$ and > 200 mmHg;
	- moderate respiratory failure: $PaO_2/FiO_2 \le 200$ and > 100 mmHg
To measure the time course of the effects of mavrilimumab on biomarkers associated with but not restricted to those possibly linked to inflammation and disease	Changes in exploratory biomarkers: - Inflammatory biomarkers (i.e. IL-6, IL-1RA, TNF-alpha, CBC and differential) - Levels of antibodies to SARS-CoV-2 / SARS-Cov-2 positivity by PCR
	Levels of anti-drug antibiodies (ADA)

4. Study design

This is a multicenter, randomized, double-blind, placebo-controlled study to assess the efficacy and safety of mavrilimumab plus standard-of-care (SOC) compared with placebo plus SOC in adult patients with COVID-19-induced pneumonia and systemic hyperinflammation. The study aims to randomize approximately 50 patients throughout the participating centers. Enrollment will stop as soon as the target number of randomized subjects is reached. Patients who meet the inclusion/exclusion criteria will be randomized in a 1:1 ratio to either mavrilimumab + SOC or placebo + SOC and can be dosed immediately after ensuring that the patient has met all eligibility criteria. Randomization will be balanced according to the following strata (in descending order of priority):

- Age (<50; 50-69; \ge 70 yo);
- Mild respiratory insufficiency (as defined by a $PaO_2/FiO_2 \ge 200$ and < 300 mmHg) vs. moderate respiratory insufficiency (as defined by a $PaO_2/FiO_2 \ge 100$ and < 200 mmHg) at randomization.

Patients in the mavrilimumab arm will be dosed on Day 1 with a dose of 6 mg/kg (using a solution with a final concentration of mavrilimumab of 50 mg/mL) infused IV over approximately 1 hour. Patients in the placebo arm will be treated with an equal amount of placebo infused IV over approximately 1 hour.

An informed consent will be obtained from patients before assessments solely required for the study are performed. Thereafter, eligibility criteria will be reviewed by study personnel. All patients with signed informed consent must be registered in an *ad hoc* prepared Interactive Response Technology (IRT) system.

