Eligible patients will have biomarker sampling according to the Assessment and Procedures Schedule (see below). Additional safety assessments will be performed approximately as described in the Assessment and Procedures Schedule. Additional follow-up visits will occur on Days 7, 14, 28, 56 and 84 either by phone if previously discharged or in the hospital if still hospitalized. If a patient is hospitalized for longer than Day 28, all invasive protocol assessments will be discontinued except at week 8 and 12, if still hospitalized. If the patient has been discharged, then patients should be phoned for follow-up and data collected as in the Assessment and Procedures Schedule. In addition, unscheduled visits are permitted at or after discharge, as needed.

Deaths and SAEs will be monitored in real time with routine pharmacovigilance and by an external, independent DSMB in order to detect any unexpected safety signal. The DSMB will function independently of all other individuals associated with the conduct of this clinical trial. Patients who do not meet the criteria for participation in this study (screen failures) may not be re-screened.

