6.7 Treatment blinding

This is a randomized double-blind placebo-controlled treatment trial. Participants, all site staff (including study investigator and study nurses) and persons performing the assessments will remain blind to the identity of the treatment from the time of randomization until database lock. Unblinding a single participant at site for safety reasons (necessary for participant management) will occur after discussion with the Promoter.

Drug product will be supplied in bulk, so an unblinded pharmacist/nurse who is independent of the study team will be required in order to maintain the blind. This unblinded pharmacist/nurse will receive the treatment arm assigned by the IRT system during the randomization transaction. Appropriate measures will be taken by the unblinded pharmacist/nurse to ensure that the treatment assignments are concealed from the rest of the site staff.

The independent DSMB will be allowed to access treatment information via a request to the randomization office for the purpose of creating, reviewing and assessing blinded interim results.

All unblinded personnel will otherwise keep randomization lists and data or information that could unblind other study team members confidential and secure until clinical database lock. Following final database lock all roles may be considered unblinded.

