For participants whose status is unclear because they fail to appear for study visits without stating an intention to discontinue or withdraw, the investigator must show "due diligence" by documenting in the source documents steps taken to contact the participant, e.g. dates of telephone calls, registered letters, etc. A participant should not be considered as lost to follow-up until due diligence has been completed or until the time point of his/her scheduled last study visit has passed.

Early study termination

The study can be terminated if any of the following happens:

- Unexpected, significant, or unacceptable safety risk to participants enrolled in the study
- Decision based on recommendations from the external data monitoring committee (DSMB)
 after review of safety and efficacy data

In taking the decision to terminate, the Promoter will always consider participant welfare and safety. Should early termination be necessary, participants must be seen as soon as possible and treated as a prematurely withdrawn participant. The investigator may be informed of additional procedures to be followed in order to ensure that adequate consideration is given to the protection of the participant's interests. The Promoter will be responsible for informing IRBs/IECs of the early termination of the trial.

Study completion and post-study treatment

Study completion is defined as when the last participant finishes their Study Completion visit and any repeat assessments associated with this visit have been documented and followed-up appropriately by the Investigator or, in the event of an early study termination decision,

CONFIDENTIAL

the date of that decision. Continuing care should be provided by the investigator and/or referring physician based on participant availability for follow-up.

10. Safety monitoring and reporting

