11.1 Determination of sample size

The sample size estimation for this study is based on the primary efficacy endpoint, time to the absence of need for oxygen supplementation. When use a two-side alpha value of 0.05 and assume the proportions of patients who do not need oxygen supplementation by day 14 are 83% and 40% for mavrilimumab and placebo arms respectively, total 28 events are required to achieve a 90% power using a log-rank test.

Approximately total 50 patients will be randomized with a 1:1 ratio to obtain the total target number of events. Analysis for treatment effect will be based on the evaluable population which includes all subjects who are randomized and receive KPL-301/placebo treatment.

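### Section 10.3 lets interim response end enrolment, against section 4's fixed target and with the full 0.05 spent on one final test; the DSMB's stated independence is also contradicted

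*Protocol*

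**What the plan says.** **Ending enrolment.** Section 4 plans about 50 randomised patients and says: "Enrollment will stop as soon as the target number of randomized subjects is reached". Section 10.3 says: "The end of enrollment will be based on interim results, with continuation of enrollment or discontinuation of the study according to the response of patients".

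**Interim review.** Section 10.2 sets up a DSMB "which in collaboration with the Writing Committee will perform safety data reviews after each increment of 10 evaluable patients has reached day 14". It adds that the board will look at progress, safety and key efficacy variables at set intervals, and may recommend continuing, changing or ending the trial. Section 9.1 allows early termination on a DSMB recommendation "after review of safety and efficacy data".

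**Final test.** Section 11.1 sizes the trial with this level: "When use a two-side alpha value of 0.05". Section 11.2 describes one primary analysis, once all patients have reached day 14. Neither section mentions interim looks.

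**Independence and blinding.** Section 4 says: "The DSMB will function independently of all other individuals associated with the conduct of this clinical trial". Section 13 gives the Writing Committee, with or in place of the principal investigator, the task of publishing the results. The synopsis calls the 10-patient reviews blinded. Section 6.7 says the DSMB "will be allowed to access treatment information via a request to the randomization office", for interim results that it also calls blinded.

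**The concern.** Sections 4 and 10.3 cannot both govern when enrolment ends. Response to treatment is efficacy, even under a heading about safety. If enrolment can end because response looks good, the final sample size depends on the data, and a test planned for a fixed sample no longer has a known level. The hazard ratio would also tend to be too favourable, because the trial would stop preferentially when the estimate is high.

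The second strand concerns who sees what. A board that is independent of everyone conducting the trial cannot also review data jointly with the group that publishes it, unless that group's access is limited. The protocol does not say who in the joint reviews may see results by arm. The primary endpoint is time to coming off oxygen, which rests partly on clinical judgement, so comparative trends should not travel beyond the board.

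**Working it through.** **1. The plan's own figure.** Section 11.1 says the day-14 proportions "are 83% and 40% for mavrilimumab and placebo arms respectively, total 28 events are required to achieve a 90% power using a log-rank test". Under proportional hazards:

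- Hazard ratio = ln(1 − 0.83) / ln(1 − 0.40) = (−1.772) / (−0.511) = 3.47, with natural log 1.244.
- Schoenfeld events = 4 × (1.960 + 1.282)² / 1.244² = 42.03 / 1.547 = 27.2, rounded up to 28. This matches the protocol. Freedman's formula gives 35, so Schoenfeld's was evidently used.
- Power at 28 events is 90.8%.
- Expected events with 25 per arm = 25 × 0.83 + 25 × 0.40 = 30.75, which covers 28.

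The 28 events therefore use the entire two-sided 0.05 in a single test. Nothing is reserved for interim looks.

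**2. Number of looks.** Reviews after each 10 evaluable patients at day 14 give four interim looks (10, 20, 30, 40). The fifth coincides with the final analysis at about 50. Section 10.3 has no schedule of its own, so taking these as its looks is an assumption.

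**3. Case A: a significant look is itself the final claim.** Assume the arms are compared at nominal two-sided 0.05 at each look, with a stop if significant. Normal theory with equally spaced looks (1,000,000 runs) gives:

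| Looks, including the final one | Overall two-sided type I error |
|---|---|
| 1 | 5.0% |
| 2 | 8.3% |
| 3 | 10.7% |
| 4 | 12.6% |
| 5 | 14.2% |

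Patient-level simulation used exponential times censored at day 14, equal hazards and an unstratified log-rank test. With five looks it gives 14.4% at a null day-14 rate of 61.5% and 14.9% at 40%, against 4.8–4.9% for the final test alone. Other runs, varying the null rate (40% to 83%) and the randomisation scheme, reach just under 18%. The fair range is about 14–18%. False claims of benefit are about 7–9%, against 2.5%.

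**4. Case B: a significant look stops enrolment, but everyone enrolled by then enters the final test.** This follows section 11.2 more closely. Patients recruited while each group of 10 is followed to day 14 dilute the chance finding. The protocol gives no accrual rate, so a range was assumed (4,000 trials per setting):

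| Days to accrue 50 patients | Type I error of the final test |
|---|---|
| 14 | 4.8–5.4% |
| 28 | 5.1–5.9% |
| 60 | 6.6–7.8% |
| 90 | 7.2–9.0% |

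A separate simulation over the same accrual range gave 4.5–8.6%. The fair range is about 5–9%.

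**5. Case C: looks can stop only for lack of effect.** Stopping whenever z < 0 at any of the first four looks, the final test at 1.96 rejects 2.2% of the time. The level is not inflated. Pooled looks that do not compare the arms do not inflate it either.

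**6. What a boundary would cost.** With p < 0.001 at four interims and 0.05 at the end (Haybittle-Peto), overall alpha is about 5.15% in normal theory. In patient-level runs it is 5.3–6.0%, where the single final log-rank test alone already gives 5.1–5.5%. For comparison, Pocock needs a nominal p of about 0.016 at every look, and O'Brien-Fleming about 0.041 at the last.

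**The case against.** A reader might infer that the final test fails its level and that the trial's error rate is 14–18%. The text does not support that. No section provides for an interim hypothesis test. The synopsis and section 6.7 use the word blinded, section 10.2 calls the reviews safety reviews, and the sentence in section 10.3 fits a stop for poor response as well as one for good response. The 10-patient interval belongs to the safety reviews, and linking it to section 10.3 is an inference. Section 11.2 also puts the primary test after all patients reach day 14, which points to case B. Section 10.3 expects the study to take roughly three months, so accrual may be fast and the inflation small. These points stand, and the size must be given as conditional.

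A reader might also infer that the blind is exposed. Section 6.7 gives treatment information only to the DSMB, keeps site staff and assessors blind until database lock, and binds unblinded personnel to confidentiality. No section says that the Writing Committee receives allocations or that its members manage oxygen. What stands is a contradiction about independence and the risk that follows from it.

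Finally, a stopping boundary may properly sit in a statistical analysis plan or DSMB charter, so its absence here is not the finding. But neither document could settle which of the protocol's two enrolment rules applies.

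**Conclusion.** The point holds as a contradiction with a conditional consequence. Sections 4 and 10.3 give incompatible rules for ending enrolment. Sections 9.1 and 10.2 permit action on efficacy, while section 11 spends all of the 0.05 once. The final test is therefore not guaranteed to hold its level, and an early stop on good response would bias the estimate upward (that bias was not quantified). If the arms are compared at 0.05 at each 10-patient look with a stop for benefit, type I error runs from about 5–9% (case B, depending on accrual) to about 14–18% (case A). It is not inflated under futility-only or pooled looks. The figures come from unstratified tests; stratifying by respiratory status should change them little.

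Separately, sections 4 and 10.2 disagree on the DSMB's independence, and the synopsis and section 6.7 leave unclear whether its reviews are blinded. This is a risk to the blind, not a breach.

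**What to change.** 1. Reconcile sections 4 and 10.3 so that one enrolment rule applies. Either:
   - state that enrolment ends at the target number and that the 10-patient reviews are for safety and cannot stop the trial for benefit, with 9.1, 10.2 and 10.3 worded to match; or
   - keep a stop for benefit and state its boundary, for example Haybittle-Peto at p < 0.001 at each interim, and say which patients enter the analysis after a stop.
2. In section 10.2, remove the Writing Committee from the DSMB reviews.
3. Make the synopsis and section 6.7 agree on whether the reviews are blinded, and state that any by-arm data are seen only by the DSMB.

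The cost is wording in the synopsis and sections 4, 6.7, 9.1, 10.2 and 10.3, and in the DSMB charter. No extra patients are needed. Under the first option the final 0.05 and the 28 events stand unchanged; under Haybittle-Peto they stand essentially unchanged.
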